7.1. General Methods

- In general, descriptive statistics for continuous variables will include number of non-missing values, arithmetic mean, SD, median, interquartile range (IQR), Q1, Q3, minimum, and maximum. Categorical variables will be summarized using percentages and frequency counts. Descriptive statistics and percentages and frequency counts will be summarized by treatment, and period, where appropriate.
- For the summary statistics of all continuous variables unless otherwise specified, minimum and maximum will be presented to the same number of decimal places as the raw data, mean, median, Q1, Q3, and IQR will be presented to one more decimal places than the raw data, and SD will be presented to two more decimal places than the raw data.
- All statistical analyses will be conducted using SAS® for Windows® Version 9.4 or higher.
- All relevant participant data will be included in listings. All participants entered into the database will be included in participant data listings.

In general, tables will be generated separately for the Two-way Crossover Periods and the Dose-Proportionality Extension Period. The tables for the Two-way Crossover Periods will present columns of treatments A, B and the tables for the Dose-Proportionality Extension Period will present columns of treatments C, D, E, F and a total column (see table shells for further details).

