7.2. Key Definitions

End of Study (EOS)

The EOS for each participant is defined as completion of the EOS Visit on Day 15 ± 2 days of the Dose-Proportionality Extension Period.

Nominal Time

Nominal time is the scheduled measurement time relative to time 0. Time 0 is the time of study drug dosing on Day 1.

Baseline Value

Baseline value will be defined as the last non-missing value recorded prior to intake of study treatment in each dosing period.

Change from Baseline (CFB)

CFB = Post-baseline value – Value at baseline

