7.4. Visit Windows

If there are multiple planned assessments for any study procedure at a given time point the latest non-missing value will be used for summarization. Unscheduled assessments will be listed and will be used to flag baseline visit if this is the last non-missing assessment before the first dose of study drug, but unscheduled assessments will not be included in the summarization.

Blood samples for assessing plasma PK/PD should be collected within $\pm 10\%$ in minutes, or 30 minutes relative to the scheduled time, whichever is less.

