12.2. Laboratory Evaluations

Safety laboratory samples for hematology, chemistry, urinalysis and coagulation will be collected at Screening, Day 1, 2, 5 and 10 of each treatment period and EOS/ET.

Samples for pregnancy test will be collected at Screening, Day -1 of each treatment period and EOS/ET.

This document is confidential.

Samples for alcohol breath test and urine drug screen will be collected at Screening and Day -1 of each treatment period.

Samples for FSH, HIV antibody/hepatitis B and C screen and serum Ceruloplasmin and serum copper will be collected at Screening only.

The following parameters will be included:

Hematology: Platelets, White blood cell count with differential (neutrophils, lymphocytes, monocytes, eosinophils, basophils), Mean cell hemoglobin, Neutrophils, Monocytes, Basophils, Hemoglobin, Mean corpuscular volume, Lymphocytes, Eosinophils.

Clinical chemistry: Blood urea nitrogen, Potassium, Creatinine, Creatine kinase, Sodium, Chloride, Glucose, HbA1c (only at screening), Bicarbonate, AST, Gamma glutamyltransferase, ALT, Alkaline phosphatase, Urea, Magnesium, Total and direct bilirubin, Total protein, Albumin, Calcium, Phosphate.

Urinalysis: Bilirubin, Glucose, Leukocytes, Nitrite, Protein, Urobilinogen, Blood, Ketones, Microscopy, if required, pH, Specific gravity, Red blood cells.

Coagulation: Prothrombin time - International Normalized Ratio, Partial thromboplastin time.

Serology: Human immune deficiency virus (HIV)-1 and HIV-2 antibodies, hepatitis B surface antigen, and anti-hepatitis C virus with confirmation by hepatitis C virus RNA

Highly sensitive serum or urine human chorionic gonadotropin pregnancy test (as needed for women of childbearing potential), Follicle-stimulating hormone (postmenopausal females only)

Alcohol breath and urine drug screen: amphetamines, barbiturates, benzodiazepines, cocaine, opiates, phencyclidine, methamphetamine, 3,4-methylenedioxy-methamphetamine, methadone, and tetrahydrocannabinol [cannabinoids].

Other tests: Serum Ceruloplasmin, serum copper

Laboratory parameter values will be graded according to the National Cancer Institute Common Terminology Criteria for Adverse Events (CTCAE).

All summaries will be based on results in SI (standard international system of units) units and will be output in the order listed above.

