Toxicity grading following the NCI CTCAE grades version 5.0 will also be derived for laboratory variables where applicable (see list below). Note, where gradings require investigator/clinical input, this will not be considered and only the numeric criteria will be used for the assignments. If this results in the criteria for more than one grade being met, the highest (worst) CTCAE grade will be assigned. For creatinine only, the criteria based on the upper limit of normal (ULN) will be used (changes compared to the baseline value will not be used), eg, CTCAE defines Grade 1 as $> \text{ULN} - 1.5 \times \text{ULN}$ or $> 1 - 1.5 \times \text{baseline}$. Only the $\text{ULN} - 1.5 \times \text{ULN}$ criterion will be used (and not the baseline criterion).

The following parameters are CTCAE gradable:

- Hematology: Absolute neutrophil count (neutrophil), total leukocytes (Leukocytes), hemoglobin (only do

This document is confidential.

the grading for Anemia, no grading for Hemoglobin increased), platelet count , Lymphocyte

- Coagulation: International normalized ratio
- Chemistry: Alanine aminotransferase albumin, alkaline phosphatase, aspartate aminotransferase, total bilirubin, creatinine, gamma-glutamyl transferase , glucose (only do the grading the Hypoglycemia, no grading for Hyperglycemia), creatine kinase.

Actual values and changes from baseline (screening) in hematology, coagulation, clinical chemistry, urinalysis will be summarized by treatment.

Shift tables for hematology, clinical chemistry and coagulation from baseline CTCAE toxicity for each visit and to the maximum grade on treatment for each parameter will be provided. Participants with both a non-missing baseline and at least one non-missing post-baseline grade will be included in the shift tables. Unscheduled data will be included in the worst case across all scheduled and unscheduled visits after the first dose of study treatment. This means that if there are CTCAE grades derived from both unscheduled and scheduled visits data per test per participant then the highest grade will be summarized.

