For non-CTCAE gradable tests, a shift table will be provided showing shifts relative to the normal ranges. This summary of normal range category changes illustrates the number and percentage of participants who fall into specified categories (Decrease to Low, Change to Normal or No Change, Increase to High) by comparing the baseline normal range category to the planned time normal range category and the worst-case normal range category. The worst-case post-baseline row will be used to summarize the participants' overall worst-case normal range category change. The determination of the worst-case takes into account both planned and unscheduled assessments. Only laboratory tests which cannot be graded per CTCAE v. 5.0 specified criteria will be included.

Participants with missing baseline value are to be assumed to have normal baseline value. Worst-case can be either High or Low. If a participant has a Decrease to Low and an Increase to High during the same time interval, then the participant is counted in both the 'Decrease to Low' and 'Increase to High' categories. If a participant was high at baseline and decreases to Low during the time interval, then the participant is counted in the 'Decrease to Low' category. Likewise, if a participant was Low at baseline and increases to High during the time interval, then the participant is counted in the 'Increase to High' category. Participants are only counted in the 'Change to Normal or No Change' category if they are:

- Normal at baseline and have no normal range High and no normal range Low values during the time interval
 - High at baseline and do not change to Low during the time interval
 - Low at baseline and do not change to High during the time interval
- Shift tables by treatment will be produced for these laboratory parameters. These tables will summarize the number of participants with each baseline grade relative to the reference ranges and changes to the worst highest grade assessed post-dose during the study.

All events of ALT $\geq 3 \times$ upper limit of normal (ULN) and bilirubin $\geq 2 \times$ ULN (> 35% direct bilirubin) or ALT $\geq 3 \times$ ULN and international normalized ratio (INR) > 1.5, if INR measured which may indicate severe liver injury (possible Hy's Law), must be reported as an SAE. Liver function results will be presented in a

This document is confidential.

summary table and eDISH (evaluation of drug-induced serious hepatotoxicity) plots.

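### SAP 12.2 takes laboratory change from Screening although SAP 7.2 sets a pre-dose baseline in each dosing period, so each treatment's descriptive change carries drift since Screening (minor)

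*SAP*

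**What the plan says.** SAP 7.2 gives one general rule: "Baseline value will be defined as the last non-missing value recorded prior to intake of study treatment in each dosing period". It makes no exception for laboratory data.

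SAP 12.2 uses another reference for laboratory change: "Actual values and changes from baseline (screening) in hematology, coagulation, clinical chemistry, urinalysis will be summarized by treatment". The same section says that safety samples "will be collected at Screening, Day 1, 2, 5 and 10 of each treatment period and EOS/ET", so Screening is not the only candidate value in any period. SAP 12.3 (vital signs) and 12.4 (ECG) refer to baseline without naming Screening. Protocol 9.4.2 plans laboratory change by study part and treatment and does not name Screening. SAP 9.6 and 14 declare no departure from the protocol.

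Three related passages bear on the same tables:

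- **Columns (SAP 7.1):** "The tables for the Two-way Crossover Periods will present columns of treatments A, B". Each of these columns pools data from Periods 1 and 2.
- **Shift tables (SAP 12.2):** these refer to baseline without the Screening qualifier, but their windows are not tied to a dosing period. One sentence reads "Unscheduled data will be included in the worst case across all scheduled and unscheduled visits after the first dose of study treatment". Another has the by-treatment tables show "changes to the worst highest grade assessed post-dose during the study".
- **Unscheduled values (SAP 7.4):** such a value is flagged as baseline "if this is the last non-missing assessment before the first dose of study drug". That describes one baseline for the whole study, not one for each period.

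**The concern.** The two baseline rules cannot both govern the laboratory change tables. A programmer who follows 12.2 literally subtracts the Screening value in all three periods. The change shown for a treatment is then the change since that treatment was given, plus whatever happened between Screening and that dose. In Period 1 the extra part is drift only. In Period 2 and the extension it also takes in any persisting effect of earlier doses.

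These columns will be read on their own. Protocol 2.3.1 names transaminase elevation, anemia and low white cell count as potential risks, to be monitored through laboratory tests. SAP 13 says that the interim analysis covers safety data and informs dosing in the planned pediatric study.

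The schedule also offers a plausible source of drift. Each period has 19 PK/PD draws before the 336-hour sample: 1 pre-dose, 9 from 1 to 24 hours, and 9 on Days 3-11. Draw volume is not given, so no effect on hemoglobin can be estimated.

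**Working it through.** The plan gives no figure of its own to reproduce. The check is interval arithmetic plus a look at which contrasts are affected.

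**Inputs**
- Screening on Days -28 to -2, and at least 14 days between doses (Protocol 4.1, SAP 4.1).
- 24 participants per sequence, 48 enrolled, at least 40 completing (Protocol 9.2, SAP 4.3).
- Laboratory samples on Days 1, 2, 5 and 10 of each period (SAP 12.2).
- Assumptions: no Day 0, and minimum washouts.

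**Step 1. Days from Screening to the dose.** Days = x + 14 × (k - 1), where x runs from 2 to 28 and k is the dosing occasion.

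| Occasion | Days from Screening to dose | Earlier doses |
|---|---|---|
| Period 1 (k = 1) | 2 to 28 | 0 |
| Period 2 (k = 2) | 2 + 14 = 16 to 28 + 14 = 42 | 1 (15 mg) |
| Extension (k = 3) | 2 + 28 = 30 to 28 + 28 = 56 | 2 (15 mg each) |

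**Step 2. What each column carries.** Let s0, s1 and s2 be the mean laboratory movement from Screening to the dose on the three occasions. For s1 and s2 this includes any effect of earlier doses.
- A and B, with 24 participants from each period: (24·s0 + 24·s1)/48 = (s0 + s1)/2. In days, (2 + 16)/2 = 9 to (28 + 42)/2 = 35, with an average of 0.5 earlier doses.
- C-F: s2, that is 30 to 56 days and 2 earlier doses.
- Gap between C-F and A/B: 30 - 9 = 56 - 35 = 21 days, and 2 - 0.5 = 1.5 earlier doses.

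**Step 3. Span of a Day 10 change** (hematology and chemistry only; a footnote to the protocol's Schedule of Activities excludes urinalysis and coagulation on Day 10). If the Day 1 sample is pre-dose, the SAP 7.2 baseline gives 10 - 1 = 9 days in every column. The Screening baseline adds the Step 1 interval:
- Period 1: 11 to 37 days. Period 2: 25 to 51 days. Extension: 39 to 65 days.
- Column averages: A and B (11 + 25)/2 = 18 to (37 + 51)/2 = 44 days; C-F 39 to 65 days.

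**Step 4. Contrasts between treatments.**
- A-B: both columns carry (s0 + s1)/2, so the difference is 0. With drop-out before Period 2, the Period 2 share is nBA/(24 + nBA) in A and nAB/(24 + nAB) in B, where nAB and nBA are the participants in each sequence with Period 2 data. At 20 and 20, both shares are 20/44 = 0.455 and the difference is still 0. In the extreme case, all 48 - 40 = 8 drop-outs leave sequence AB before Period 2. The shares are then 24/48 = 0.50 and 16/40 = 0.40, and the contrast carries 0.10 × (s1 - s0).
- Among C-F: every arm carries s2 in expectation, because participants are re-randomised on Day 1 of the extension.

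**Step 5. Drift or earlier doses?** Protocol 4.2 expects more than about 99.2% of plasma total Mo to be gone after 14 days, which leaves under about 100 - 99.2 = 0.8%. That does not exclude a lasting laboratory effect, but it makes drift the firmer component.

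**The case against.** The case for leaving this alone is strong on consequences. Safety is descriptive only. Actual values, which need no baseline, are tabulated alongside, and all laboratory results and grades are listed. No primary or secondary endpoint is touched. Screening is also a legitimate drug-free reference, and declaring it as an exception would remove the contradiction. All of this stands, and it is why the point is minor. A declared exception would still leave drift in the main table, however, and the SAP has not declared one.

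The remedy also depends on an unconfirmed detail. The Schedule of Activities grid is not in the supplied text, and Protocol Table 2 lists no safety laboratory tests. The order of procedures in Protocol 8.2 applies only to procedures scheduled together. The 10-hour fasting rule does not settle it, because participants stay fasted for at least 4 hours after dosing (Protocol 6.1). Hence the condition in the fix. If the Day 1 sample were post-dose, the two baselines would usually coincide in Period 1, but would still differ in Period 2 and the extension.

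A reader might infer more than the documents support:

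- **That the A-B comparison is biased.** Step 4 shows that it is not, unless drop-out is very one-sided.
- **That the shift tables also use Screening.** Baseline is a defined term in SAP 7.2, and the Screening qualifier appears only in the change-from-baseline sentence. The default reading for the shift tables is therefore 7.2. A statement to that effect is a clarification.
- **That worst grades in an A or B column would run from Period 1 to the end of the study.** SAP 7.1 generally separates crossover and extension tables, so extension samples would not normally enter a crossover table. What stays loose is the window between Periods 1 and 2 within the crossover, and the table shells that might settle it were not supplied.
- **That laboratory carry-over has been shown.** No document gives evidence of it.

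**Conclusion.** The conflict between SAP 12.2 and SAP 7.2 is real, and the laboratory rule is wrong as written: it replaces the defined baseline without declaring or justifying an exception. Followed literally, it puts 2-28, 16-42 or 30-56 days of pre-dose drift into the absolute change, depending on the period. Outside Period 1 it also adds any effect of one or two earlier doses. Setting C-F beside A/B would carry a further 21-day difference, but the SAP plans no such laboratory comparison.

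These figures are elapsed times and dose counts. They are not laboratory distortion, whose size the documents do not allow anyone to compute. They assume minimum washouts, no Day 0 and balanced sequences; longer washouts lengthen the Period 2 and extension intervals. Severity is minor, because the between-treatment contrasts are protected and the tables are descriptive.

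**What to change.** 1. **SAP 12.2, change tables:** replace the Screening reference with the SAP 7.2 pre-dose baseline of each dosing period, after confirming that the Day 1 safety sample is drawn before dosing. Use Screening only as a fallback when no later pre-dose value exists.
2. **SAP 12.2, shift tables:** state that the CTCAE and normal-range shift tables use the same baseline, and limit their worst-grade windows to the dosing period of the treatment shown.
3. **SAP 7.4:** for unscheduled values, refer to the dose in each dosing period, not only the first dose of the study.
4. **Keep one table of change from Screening, labelled as such.** A period baseline subtracts any effect that persists from an earlier dose, so the drug-free reference remains informative.

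The cost is SAP wording, one extra descriptive table and the check on Day 1 timing. No new samples are needed if that timing is confirmed.

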12.3. Vital Signs

Systolic blood pressure (mmHg), diastolic blood pressure (mmHg), heart rate (bpm), respiratory rate (breaths per minute) and temperature (degree Celsius) will be measured at Screening, Day 1 (Pre-dose, 6 hours, 12 hours), Day 2, Day 5, Day 11 of each treatment period and EOS/ET.

If vital sign results are abnormal, 2 additional readings will be taken. The mean of the 3 replicates will be recorded in the case report form (CRF) and used for the analysis.

Actual values and changes from baseline in vital sign measurements will be summarized by treatment.

Note temperature will be reported in centigrade. Any conversions required will be as follows:

Temperature (in °C) = 5/9 (Temperature [in °F]-32).

All vital signs will be provided in data listings.

12.4. ECG

The ECG parameters include heart rate, PR, RR, QRS, QT, and corrected QTcF intervals.

12-lead ECGs in triplicate will be taken at Screening and on Day 1, 0.5 hours pre-dose and at 6 hours post-dose on Day 1 of the first dosing period and Day 1 of the Dose-Proportionality Extension Period. 12-lead ECGs should be measured after a minimum of 5 minutes in supine position. The average of the triplicate ECG readings at the time points collected will be calculated and used in the analyses.

Actual values and change from baseline of these average ECGs will be summarized by treatment.

All ECG parameters, including all single ECG measurements, but also the mean value and overall ECG evaluation will be provided in data listings.

12.5. Physical Examination

A full physical examination will be performed at Screening and on Day -1 of the 2 dosing periods. A symptom-driven physical examination of relevant body systems may be performed at other times, at the Investigator's discretion.

Physical examination data will be listed.

This document is confidential.

13. Interim Analyses

An interim analysis is planned after completion of the Two-way Crossover Periods of the study (Group 2 discharged after completing Period 2) and after the bioassay results for plasma total and PUF Mo and Cu results become available.

The interim analysis will capture all PK, PD, and safety data and provide comparative relative bioavailability data of the 2 treatments to decide on safe and appropriate dosing with the 1.25 mg EC mini-tablets in the planned Study ALXN1840-WD-302 in pediatric patients with WD.

This document is confidential.

14. Changes from Analysis Planned in Protocol

Not Applicable.

This document is confidential.

15. Reference List

- EMA. Committee for medicinal products for human use (CHMP): Guideline on the Investigation of Bioequivalence (CPMP/EWP/QWP/1401/98 Rev. 1). Available from: http://www.ema.europa.eu/docs/en_GB/document_library/Scientific_guideline/2010/01/WC500070039.pdf. 2010.
- Newlands A. Statistics and Pharmacokinetics in Clinical Pharmacology Studies. SAS Conference Proceedings: Pharmaceutical Users Software Exchange; Dublin, Ireland, 2006.

This document is confidential.

16. Quality Control

SAS programs are developed to produce output such as analysis data sets, summary tables, data listings, figures or statistical analyses. An overview of the development of programs is detailed in Syneos Health Developing Statistical Programs SOP (3907) .

Syneos Health Developing Statistical Programs SOP (3907), Conducting the Transfer of Biostatistical Deliverables SOP (3908) and the SAS Programming and Validation Plan describes the quality control procedures that are performed for all SAS programs and output. Quality control is defined here as the operational techniques and activities undertaken to verify that the SAS programs produce the output by checking for their logic, efficiency and commenting and by review of the produced output.

Syneos Health SOP Pharmacokinetic and Related Data Analysis (3913) describes the process for the interaction between the Biostatistics and Pharmacokinetics departments for the analysis of pharmacokinetic and pharmacodynamic data.

This document is confidential.
